Protocol Number: NP-PWD-02

Protocol Date and Version #:09 February 2024, V2

PROTOCOL TITLE: A Case-Control Study of Negative Pressure Platform Wound Devices (NP-PWD) for Skin and Soft Tissue Defects

SECTION A: RESEARCH TEAM AND LOCATIONS

A1. RESEARCH TEAM

Study Role	Institution/Company and Contact Information
Principal Investigator and Sponsor	[name] Principal Investigator The Metis Foundation [contact] [contact]
Key Research Personnel	[name] Research Project Manager The Metis Foundation [contact] [contact]
	[name] Clinical Research Nurse The Metis Foundation [contact] [contact]

A2. RESEARCH LOCATIONS

Northeast Baptist Hospital

A3. MULTISITE RESEARCH N/A

B. SOURCE OF EXTERNAL FUNDING

Applied Tissue Technologies

C1. HYPOTHESIS/STUDY SYNOPSIS

Hypothesis: The Negative Pressure Platform Wound Device (NP-PWD) technology is a feasible alternative to manage skin and soft tissue defects as compared to standard of care, KCI Wound VAC granulofoam.

Study Synopsis: This study will demonstrate the effectiveness of the NP-PWD therapy in managing complex wounds and improving wound healing parameters as compared to standard of care.

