A study of 24 completed subjects will be conducted by enrolling patients who are requiring treatment for open skin and soft tissue defects. Patients will be screened for inclusion criteria and asked to consent to participate in the study. Following consent subjects will be randomized to receive treatment of one of the two study arms. Arm 1, the standard of care arm, will receive KCI Wound VAC Granulofoam. Arm 2, the study arm, will receive treatment with NP-PWD. Prior to the initial application, wound evaluations and photography will be completed to include assessment of infection with wound swabs. The wound dressing will be assessed for the need for change every 2-3 days and changed if clinically indicated (following each device IFU). Subjects will be followed for up to nine days post initial application. At minimum, the randomized treatment will be applied for 2 days after initial application for a subject to be considered completed. Subject who do not complete the treatment course (minimum of 2 days of treatment), may be replaced per investigators discretion. Follow up data will be gathered at each change/removal of the NP-PWD or Wound VAC. The data collected will include indications for dressing change, dressing change process, photographs and assessments for wound healing, infection, and adverse events. Gathered clinical data of the enrolled subjects will be used to evaluate the feasibility in using the NP-PWD device for wound healing management.

C2. BACKGROUND

Open complex wounds are a prominent issue, as unhealed or untreated wounds pose a risk of microbial infection. The Negative Pressure Platform Wound Device or NP-PWD, is an innovative therapy which uses a patented dressing to promote healing by creating a vacuum (negative pressure) at the wound site without the use of an intervening foam dressing. This pressure promotes granulation of the skin, forming new connective tissue and blood vessels, removes or inhibits microbial and infectious agents, as well as pulls wound edges together for closure. Although this therapy is evolving, the review of elements and effects on wounds is still uncertain and requires further studies regarding the mechanism and use of NP-PWD in wound healing.

C3. OBJECTIVES/STUDY GOALS

This study is intended to evaluate the feasibility of the NP-PWD as compared to SOC for the treatment of wound healing through assessment of healing time, feasibility of application, patient

comfort, and adverse events.

Primary:

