A copy of the IRB-approved informed consent document will be given to the potential subject for their review and ample time will be given for their decision making. If the potential subject decides to participate, the IRB-approved informed consent document will be signed and dated appropriately by all persons required on the document. The original signed consent document will be kept in the study files; a copy will be given to the subject and a copy will be placed in the subject's medical record.

Study procedures will not begin until eligibility is determined, and the informed consent process is completed. Patients who sign the informed consent form are considered to be enrolled. If a patient signs the consent but is not randomized into the study, the patient is considered a screen failure.

Subjects will be enrolled for up to 9 days following application of the NP-PWD or Wound VAC. At minimum, the randomized treatment will be applied for a minimum of 2 days after initial application for a subject to be considered completed. Subject who do not complete the treatment course (minimum of 2 days of treatment), may be replaced per investigators discretion.

Activities to be completed for each visit are as follows:

Treatment (Day 0): Screening, consent, documentation of baseline demographics, medical history and physical, measurement and photography of wound, wound swab for colony forming unit count, randomization, and application of NP-PWD or Wound Vac according to randomization.

Follow-up visits:

At each follow-up visit the study wound will be assessed for the need for dressing change (every 2-3 days) and changed if clinically indicated (following the respective device's IFU). The study wound sites will be assessed for signs of infection, erythema, itching, drainage, quality of closure and pain.

Follow-up (Visit 2): Assessment of need for dressing change and completion of change of treatment dressing if necessary. Should the study subject's wound indicate continuation of negative pressure wound therapy a second application of the randomized treatment may be applied. If the subject no longer requires negative pressure wound therapy, the therapy will be

discontinued. Wound assessments, measurements, photographs, assessments for adverse events will all be completed and documented.

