All pertinent data will be analyzed using descriptive and correlational statistics as appropriate to compare those patients who were treated. Overall standard descriptive statistical methods will be used to analyze other data; any categorical variables will be compared via chi square analysis while continuous variables will be compared via student-t test or Wilcoxon test as appropriate. We plan to perform a forward stepwise logistic regression. The available data including patient specific data as well as treatment variables will first be evaluated using a univariate analysis for possible significant risk factors. These will then be analyzed using a multiple logistic regression analysis and tested for interaction.

D1. RISK/ SAFETY INFORMATION

Risks of harm, measures to reduce the risks of harm and benefits of participation

Risks of Harm

Research Procedure Name: Application of NP-PWD or Wound VAC

Research Procedure Description: Application of a NP-PWD or Wound VAC onto open wound.

Research-related Risks

- Itching, swelling and redness.
- Infection.

- Poor healing.

Measures to Minimize Risks of Harm: (Precautions, safeguards): Application of the NP-PWD or Wound VAC will be performed in a controlled clinical setting. Throughout the course of the study, the NP-PWD or Wound VAC will only be applied by trained professionals and the site will be monitored for signs adverse reactions such as infection or poor healing.

D2. MONITORING AND REPORTING OF ADVERSE EVENTS/ SERIOUS ADVERSE EVENTS

Monitoring

Data collected on the subjects will be entered into a data spreadsheet that will be verified routinely by designated study personnel for accuracy and completeness. The study will be conducted in compliance with any applicable laws and regulations. Designated study staff, for accuracy and completeness, will verify data collected. All regulatory and subject files will be maintained in accordance with any applicable regulations.

The principal investigator will be responsible for the protocol safety monitoring. The PI will make study documents (e.g., consent forms, data pulls) and pertinent hospital or clinical records readily available for inspection by the IRB and oversight staff for confirmation of the study data.

Adverse Events

Adverse events that are anticipated in this patient population include those associated with wound healing.

Unexpected adverse events and unanticipated problems

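### Free improvement: no analysis of wound size uses the Day 0 measurement as a covariate, although it is taken before randomization

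*Combined protocol and SAP*

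**What the plan says.** The Data Analysis section gives one rule for every continuous outcome: "continuous variables will be compared via student-t test or Wilcoxon test as appropriate". It names no covariate, scale or time point, and does not say whether a follow-up value, a change or a percent change is tested. The only multivariable method is separate: "We plan to perform a forward stepwise logistic regression". That needs a binary outcome, which is not named, so it does not adjust a continuous wound size.

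Section D lists the Day 0 activities in this order: "measurement and photography of wound, wound swab for colony forming unit count, randomization". The wound is therefore measured before allocation. At Visit 2, "Wound assessments, measurements, photographs, assessments for adverse events will all be completed and documented". Visits 3 and 4 repeat the measurements but are optional.

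The entry criteria in C4 require an open defect needing treatment and set no size limit. Stratified randomization is not mentioned. The synopsis in C1 sets out to show effectiveness in managing complex wounds and "improving wound healing parameters as compared to standard of care". Wound size is not a named endpoint in C3: the primary objective is usability and feasibility, and the secondary ones are readiness for closure, colony counts, ease of use and tolerability.

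**The concern.** A wound's size two or three days into treatment is likely to depend heavily on its size at the start. With no size limit at entry, starting sizes may vary widely. A two-sample test on follow-up size would then carry that between-patient variation in its error term, although the plan already collects the measurement that could remove it.

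Two things are at stake in a 24-subject trial. A real difference in wound size could be missed for lack of precision. A chance difference in starting size between arms could also pass into the follow-up comparison and be read as a device effect, or hide one. Because the variable and its scale are left open, they could be chosen after the data are seen.

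**Working it through.** **The plan's own figure.** C1 states "A study of 24 completed subjects will be conducted". No alpha, power, effect size or SD accompanies the 24, so it cannot be reproduced.

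**Inputs.**
- From the documents: 24 completed subjects, two randomized arms, measurement at Day 0 and Visit 2 (Day 2-3).
- Assumed: 1:1 allocation (12 per arm; no ratio is stated), two-sided alpha 0.05, log-normal area with SD of log area 0.7 to 1.0 at both times, baseline/follow-up correlation ρ from 0.5 to 0.95, and an area 40% smaller with NP-PWD.

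**Step 1. Effect on the log scale.** |ln 0.60| = 0.511. In SD units this is 0.511/0.7 = 0.73 and 0.511/1.0 = 0.51.

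**Step 2. Error variance per subject, in units of SD².**
- Raw follow-up value: 1, whatever ρ is.
- Change from baseline: 2(1 − ρ).
- ANCOVA on the baseline value: 1 − ρ².

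| ρ | Raw | Change | ANCOVA |
|---|---|---|---|
| 0.5 | 1 | 1.00 | 0.75 |
| 0.8 | 1 | 0.40 | 0.36 |
| 0.9 | 1 | 0.20 | 0.19 |
| 0.95 | 1 | 0.10 | 0.098 |

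Against the raw test, ANCOVA is worth a sample-size factor of 1/(1 − ρ²): 1.33 at ρ = 0.5, 2.78 at 0.8 and 10.26 at 0.95.

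**Step 3. Power by simulation** (40,000 trials per setting; t-tests on 22 degrees of freedom, ANCOVA on 21). Each cell gives SD 1.0, then SD 0.7.

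| ρ | Raw log area | Log change | ANCOVA on log area |
|---|---|---|---|
| 0.5 | 22%, 40% | 22%, 40% | 27%, 48% |
| 0.8 | 22%, 40% | 47%, 77% | 49%, 79% |
| 0.9 | 22%, 41% | 76%, 97% | 76%, 97% |
| 0.95 | 22%, 40% | 96%, >99% | 96%, >99% |

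For a 25% smaller area, the raw test has about 10-16% power. ANCOVA has 19-85% at ρ = 0.8-0.95 and 12-19% at ρ = 0.5.

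**Step 4. Chance imbalance.** The standard error of the difference in baseline means is √(2/12) = 0.41 SD. The probability of a difference above 0.5 SD in either direction is 2[1 − Φ(0.5/0.408)] = 22%.

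**Step 5. Does the scale of the change matter?** Assume instead area reductions of 15% (control) and 30% (NP-PWD), baseline log-SD 0.8-1.0 and SD of log change 0.15-0.25. A t-test then has about 5-7% power on raw area, 16-32% on absolute change and 44-86% on the log ratio.

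**The case against.** The strongest reply is that the plan never commits to testing raw follow-up size. A reader might infer that it does, but a t-test or Wilcoxon test on change or percent change fits the wording equally well. On log change, at a correlation of 0.8 or more, that test comes within about 2 points of ANCOVA in Step 3. This stands: the factor of 2.8 to 10 is the distance from one possible reading at high correlation, not a loss that the plan has fixed. It does not close the gap. Nothing commits the sponsor to log or percent change, absolute change does much worse in Step 5, and at correlation 0.5 log change gains nothing over the raw value.

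A reader might also infer that starting size will swamp the device effect. The documents give no SD or correlation to support that as a fact. At correlation 0.5 the gain from adjustment is small: 40% to 48% power at SD 0.7.

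The assumed effects are large against an active negative-pressure comparator at Day 2-3. For smaller ones, adjustment may still leave power low.

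Finally, wound size is not a named endpoint in a feasibility study that claims no power. This also stands and limits the weight of the point. It remains relevant because C1 promises a comparison of healing parameters and the measurements are collected at every visit.

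**Conclusion.** The point holds as a free improvement. No baseline adjustment is specified for a continuous wound measurement, although the Day 0 value is available and the logistic regression cannot supply the adjustment. If raw follow-up size is tested, the loss is large at correlation 0.8-0.95 and small at 0.5. ANCOVA is never materially worse than the raw test or the log-change test in the settings checked. These sizes rest on the assumed 12 per arm, SDs, correlations and effects, none of which the documents state.

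It would be wrong to conclude that the planned test is biased or invalid. Under randomization ("Following consent subjects will be randomized to receive treatment of one of the two study arms") the unadjusted comparison is valid and unbiased on average. The cost is precision and exposure to chance imbalance in a supportive healing measure. The primary objective is unaffected.

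**What to change.** Add to Data Analysis: *Wound size at Visit 2 will be compared between arms by ANCOVA on the log scale with arm and log Day 0 size as terms; the adjusted ratio and its 95% confidence interval will be reported as a supportive wound-healing analysis.*

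State which dimension wound size means (for example area), since the protocol speaks only of measurements. Visit 2 is the natural time point because it is the only follow-up visit that is not optional. A rank-based ANCOVA can serve as a sensitivity check.

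The cost is a sentence or two of analysis wording. No new data, visits or subjects are needed, and the choice of variable and scale is settled before results are seen.

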To determine the usability and feasibility of NP-PWD in comparison to SoC

Secondary:

- To evaluate and compare wound readiness for closure between study wounds treated with NP-PWD versus SoC
- To evaluate colony forming units present on study wounds before and after treatment(s)
- To evaluate the ease of use of the product by healthcare providers
- To evaluate tolerability of the product by patient subjects

C4. SUBJECT SELECTION

Twenty-four (24) patients, 18 years of age or older, who are requiring treatment for open skin and soft tissue defect at a hospital within the Baptist Health System will be recruited for participation in this study. Potential subjects must meet the following inclusion and exclusion criteria to be included in this study.

Inclusion Criteria

All subjects enrolled must meet ALL the following criteria:

1. Patients 18 years of age or older of either gender
2. Have an open skin or soft tissue defect requiring treatment

Exclusion Criteria

Subjects who meet any of the following criteria will be excluded from the study:

1. Active malignant disease at the study site
2. Any concomitant medications or co-morbidities that, in the opinion of the investigator, may interfere with device use
3. On any investigational drug(s) or therapeutic device(s) to the study site in the last 30 days or any previous enrollment in this study
4. Pregnant at enrollment

When a potential subject is identified a member of the research staff will approach the potential subject or their legally authorized representative (LAR) and introduce the proposed study. If a potential subject or their LAR expresses interest in participation in the study, the PI or designated study personnel will proceed with the informed consent process for potential enrollment.

D. STUDY PROCEDURES/ RESEARCH METHODS

Informed consent of potential subjects will be done in a quiet and private area of the patient care setting (hospital or clinic office) to ensure patient confidentiality. The PI or designated study staff will discuss and explain elements of the study with the informed consent document. The PI or designated study staff will also be available to answer questions for the potential subject.

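### Univariate screening, forward stepwise logistic regression and interaction tests on 24 subjects can readily report noise as risk factors, and no rule keeps the randomised arm in the model

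*Combined protocol and SAP*

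**What the plan says.** The Data Analysis paragraph of section D first plans simple comparisons: "any categorical variables will be compared via chi square analysis while continuous variables will be compared via student-t test or Wilcoxon test as appropriate". It then says "We plan to perform a forward stepwise logistic regression". Of the inputs it says that the "available data including patient specific data as well as treatment variables will first be evaluated using a univariate analysis for possible significant risk factors", and it continues: "These will then be analyzed using a multiple logistic regression analysis and tested for interaction".

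The sample size is in C1: "A study of 24 completed subjects will be conducted by enrolling patients". Subjects are randomised to two arms and no allocation ratio is given. The primary objective in C3 is "To determine the usability and feasibility of NP-PWD in comparison to SoC"; one secondary objective is "To evaluate and compare wound readiness for closure between study wounds treated with NP-PWD versus SoC".

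The plan does not state the dependent variable of the logistic model, the candidate list, the screening or entry thresholds, or the interaction terms. It does not label the regression exploratory, and it does not say that the randomised arm stays in the model. Treatment variables are among the items screened, but it is unclear whether that term means the randomised arm.

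**The concern.** A significance screen followed by forward selection, on a sample this small with an open candidate list, will often find something by chance. The plan's own wording would present it as a risk factor.

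The arm is exposed in either reading. If it is a candidate, it is kept only when significant, and the estimate then reported is one that has passed a filter. If it is not a candidate, the plan's only multivariable analysis gives no adjusted arm effect. Interaction terms between selected variables, fitted to 24 subjects, may have no finite estimate.

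Section D4 intends the findings for presentation or publication, so a chance association could be published without a caution attached.

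**Working it through.** **Inputs.** From the documents: 24 completed subjects, two randomised arms. Everything else is assumed because the plan is silent: 12 per arm; candidates are the arm plus 5, 9 or 14 noise covariates, about half binary (prevalence 40%) and half normal; likelihood-ratio tests; screen and entry both at 0.05 or both at 0.10. The plan gives no figure of its own to reproduce. The smaller outcome class has at most 24/2 = 12 subjects, so ten candidates would mean at most 12/10 = 1.2 events each.

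**1. Noise in the final model (no true effects, 50% event rate).** For m independent tests at level α, the chance that at least one passes is 1 − (1 − α)^m. The simulation of the full screen-and-enter procedure used 3,000 trials per cell.

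| Noise covariates | 1 − 0.95^m | Simulated, 0.05 | Simulated, 0.10 |
|---|---|---|---|
| 5 | 22.6% | 27.1% | 45.7% |
| 9 | 37.0% | 42.8% | 67.4% |
| 14 | 51.2% | 57.9% | 79.4% |

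The simulated 0.05 figures exceed the formula partly because the likelihood-ratio test is slightly liberal here: its exact size for a 12/12 binary factor at a 50% event rate is 6.4%. A separate simulation with 5, 10 and 15 noise covariates, 6 or 12 events, a screen at 0.05 or 0.20 and entry at 0.05 gave about 25–28%, 45–47% and 59–62%.

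**2. Arm left out (true rates 30% vs 60%).** One exact likelihood-ratio test of the arm at 0.05 fails in 64.2% of trials; that is the sample size alone. Screen plus stepwise leaves the arm out in 65.5%, 68.8% and 69.6%, so selection adds about 1 to 5 points. With one prognostic covariate (log odds ratio 1 per SD, ten candidates) the figures are 74.1% for the screen alone and 78.2% for the full procedure.

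**3. Size of the arm estimate when it passes.** The true odds ratio is (0.6/0.4)/(0.3/0.7) = 3.5. Enumerating all 13 × 13 tables, the arm passes 0.05 with probability 0.358. The smallest passing odds ratio above 1 is 6.0, for example 4/12 vs 9/12: (9 × 8)/(4 × 3) = 6. The median given a pass is 10, for example 4/12 vs 10/12: (10 × 8)/(4 × 2) = 10. At a 0.10 or 0.20 screen the median is 7. Pearson chi-square gives the same medians, so this is the effect of filtering on significance at 12 per arm and is not peculiar to stepwise entry.

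**4. Interactions and estimability.** Separation was checked by linear programming, 1,000 trials per cell, at 0.05, for event rates of 50%, 30% vs 60%, and 25%.
- Two or more variables reach the final model in 3–17% of trials. When they do, at least one pairwise interaction has no finite estimate in 43–60% (50% event rate, or 30% vs 60%) or 73–82% (25% event rate). That is 2–14% of all trials, or 3–29% with thresholds of 0.10.
- If a model with arm, a binary factor of 40% prevalence and their interaction is fitted, it has a finite estimate only when all four cells are occupied and each contains both outcomes. The exact probability that this fails is 0.298, 0.448 and 0.646 for the three event-rate settings. For a continuous factor it is 1–12%.
- The selected main-effects model itself has no finite estimate in 2–10% of trials, and in 12–30% at a 25% event rate.

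**5. The replacement model.** Firth logistic regression with the arm and one continuous covariate, 95% profile interval, 400 runs per setting. For event rates of 25–60%, coverage is 0.950–0.968, the median ratio of upper to lower limit is 27–45, and limits are finite in 99.5–100%. Near 10% or 90%, coverage is 0.968–0.990, the median ratio is 344–1,762, and limits are finite in 98.3–99.8%.

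**The case against.** The strongest reply is that little rests on this regression. The primary objective is usability and feasibility, the regression is not called primary, and the direct comparisons of the arms are planned separately. Under randomisation those comparisons need no covariate adjustment to be unbiased. The plan does not say that the regression is meant to estimate the treatment effect. All of this stands, and it limits the point to the regression.

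Second, losing the arm is mostly a power problem (64% before any selection), and the inflated odds ratio arises equally with a chi-square filter. This also stands. What remains is that forcing the arm in, and reporting it regardless of its p-value, removes both the extra loss and the filter.

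Third, most of the noise rate comes from multiple testing at the screen and forward entry adds little, while interaction failures are uncommon in absolute terms. That is correct, but the screen is part of the stated procedure and nothing in the plan limits or labels its output.

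Fourth, every percentage rests on assumed inputs. This is true: the documents fix the direction but not the size. The gap also leaves outcome, candidates and thresholds open to choice after the data are seen.

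**Conclusion.** The concern holds. Followed as written, the regression has a substantial chance of reporting a noise covariate as a risk factor: 27–58% at thresholds of 0.05 and 46–79% at 0.10, for 5 to 14 noise candidates. Whether it exceeds one half depends on the candidate count and threshold. These figures assume 12 per arm, independent covariates, a 50% event rate and likelihood-ratio tests.

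No rule keeps the arm in the model. Selection adds about 1–5 points to a 64% loss that is due to the sample size, and any arm estimate kept for significance is exaggerated (median odds ratio 10 against a true 3.5 in the 30% vs 60% case). Interaction failure is a smaller matter overall.

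Confidence is high in the direction, not in any single percentage. The point does not undermine the trial or its direct arm comparisons, but it should be fixed because the remedy is cheap.

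**What to change.** Delete the univariate screen, the stepwise selection and the interaction tests. Deletion alone removes the defect. Only adding an exploratory label would temper the claims but still produce a list of p-values.

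If an adjusted arm effect is wanted, replace the search with one pre-specified model:
- **Outcome.** Name one binary outcome built from what the visits already record: "The study wound sites will be assessed for signs of infection, erythema, itching, drainage, quality of closure and pain", plus wound measurements. If readiness for closure is chosen, define its criteria from these assessments.
- **Time point.** Fix it in advance. Visit 2 is the only follow-up that is not optional and gives a common time. If final device removal is used, state that the day varies from 2 to 9 and that wound status may be tied to the reason for removal.
- **Model.** Randomised arm always included, at most one pre-named baseline covariate (for example log baseline wound area), and a small-sample method such as Firth penalisation. Report the arm odds ratio and 95% interval whatever its p-value.
- **Sparse data.** If the smaller outcome class has fewer than about five subjects (a judgement, not a derived limit), report counts with exact intervals only.
- **Other covariates.** Label as exploratory and descriptive, without p-values.

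The cost is three rewritten sentences and one outcome definition. No visits are added; readiness for closure may need one more worksheet item. The sponsor gives up a risk-factor list and gets a wide interval. The change does not restore power; it removes the selection and the estimation failures.
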